Study Procedures

- 1. Antepartum patient diagnosed with a hypertensive disorder in pregnancy.
- 2. Patient approached for study participation and informed consent obtained if interested.
- 3. Patient develops severe range BP (SBP>160 and/or DBP>110) with increased pulse pressure (>60mmHg). This will be considered baseline BP.
- 4. When ordering provider's choice of antihypertensive, pharmacy notified that patient is study participant and randomizes patient by choosing from sequential opaque envelope.
- 5. a. Patient randomized to treatment arm and receives 40mg /4mL IV furosemide in addition to usual antihypertensive.
 - b. Patient randomized to placebo and receives 4mL normal saline in addition to usual antihypertensive.
- 6. Blood pressure check every 15 minutes after administration of furosemide/placebo for four recordings (15, 30, 45, 60 minutes)

2. Data analysis

Specify statistical and analytical methods (statistical power, sample size, significance level, etc.).

The primary outcome variable is reduction in mean systolic BP during the 1-hour period after drug administration. BP will be taken every 15 minutes for 1 hour and averaged. Intention-to-treat analysis will be performed. This study will use a two-sided t-test with the null hypothesis set at the standard significance level (p –value < 0.05), to determine if the addition of furosemide to usual antihypertensive significantly reduces blood pressure.

Change in average BP from baseline will be tested comparing the group receiving furosemide and the group receiving placebo using Mann-Whitney U, as BP usually presents as a non-parametric continuous variable. Multivariate regression will be used to adjust for potential confounders, such as maternal age, BMI, diabetes, baseline BP, antihypertensive chosen by the primary obstetrician, number of doses of antihypertensive, and gestational age. Comparative testing will be done to explore differences between the furosemide and placebo groups. Continuous variables satisfying the assumption of normality will be tested using the Student t-test and means and standard deviations will be reported. Otherwise, variables will be tested using the Mann-Whitney U test and will be reported using medians and interguartile ranges. The x2 or

Version 2

Protocol Number I

Fisher exact test will be utilized to test categorical variables and sample sizes and percentages will be reported.

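### The Data analysis section sends the primary blood pressure comparison to both a t-test and Mann-Whitney U, and leaves the choice until after data collection without a criterion

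*Combined protocol and SAP*

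**What the plan says.** All of the following is in Section III.2 (Data analysis) unless stated.

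- **Outcome.** "The primary outcome variable is reduction in mean systolic BP during the 1-hour period after drug administration". Readings at 15, 30, 45 and 60 minutes are averaged. The primary objective in Section I.1 speaks of reduction from baseline.
- **First test.** "This study will use a two-sided t-test with the null hypothesis set at the standard significance level". No condition is attached.
- **Second test.** The next paragraph states: "Change in average BP from baseline will be tested comparing the group receiving furosemide and the group receiving placebo using Mann-Whitney U". The reason given is "as BP usually presents as a non-parametric continuous variable". Again there is no condition.
- **Regression.** "Multivariate regression will be used to adjust for potential confounders, such as maternal age, BMI, diabetes, baseline BP". The list goes on to the antihypertensive chosen, then "number of doses of antihypertensive, and gestational age". The model is not called primary, supportive or sensitivity.
- **General rule.** Continuous variables that satisfy normality get a t-test. "Otherwise, variables will be tested using the Mann-Whitney U test and will be reported using medians".
- **Power paragraph.** The trial is sized on a two-group t-test under normality and common variance: SD 20 mmHg, difference 15 mmHg, 80% power, 28 per arm. The paragraph ends by leaving the normality check and the choice of test until the data have been collected.
- **Timing of randomisation.** Section III.1, Study Procedures, step 4: when the antihypertensive is ordered, "pharmacy notified that patient is study participant and randomizes patient by choosing from sequential opaque envelope".

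**The concern.** Two sentences give the same comparison to two different tests. A third statement, the normality rule, would override both if it governs the primary outcome, and it cannot be applied as written because it names no test of normality and no cut-off. After the data are seen, either result could be presented as the planned one.

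The two tests also answer different questions. The objective and the 15 mmHg target are differences in mean pressure. Mann-Whitney U reported with medians gives no estimate of that difference. The text is at odds with itself on shape too: it expects blood pressure to be non-normal when choosing Mann-Whitney U, and assumes normality when sizing the trial.

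The dose covariate is a separate matter. Randomisation takes place when the antihypertensive is ordered, so doses can be given afterwards and their number can depend on whether furosemide worked. Adjusting for a consequence of treatment can bias the estimated treatment effect.

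**Working it through.** **1. The plan's own figure.** Inputs from the power paragraph: difference 15, SD 20, two-sided alpha 0.05, power 80%.

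n per arm = 2 × [SD × (z₀.₉₇₅ + z₀.₈₀) / difference]² = 2 × [20 × (1.960 + 0.842) / 15]² = 27.9, so 28 per arm and 56 in total. With 80% retention (Section II.1), 56 / 0.8 = 70. The stated figures reproduce.

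This is the normal approximation (power 80.1%). With the noncentral t, noncentrality = 15 / (20 × √(2/28)) = 2.81 on 54 df, power at 28 per arm is 78.7%, and 29 per arm give 80.1%.

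**2. What the open choice does to the result.** Simulation with 28 per arm and SD 20 applied to the change score, pooled t-test and Mann-Whitney U (asymptotic, continuity-corrected). The lognormal shapes are assumptions; the documents give no skew.

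No true effect, normal data:
- t-test 5.0%, Mann-Whitney U 4.8%
- better of the two 5.8–5.9%
- a fixed rule (Shapiro-Wilk at 0.05 in each arm, assumed because none is named) 5.2%

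True 15 mmHg effect:

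| Data | Trials in which the tests disagree |
|---|---|
| Normal | about 5.6% (1 in 18) |
| Assumed mild skew, lognormal sigma 0.25 | about 7% (1 in 14) |
| Assumed strong skew, lognormal sigma 0.5 | about 12% (1 in 8) |

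With normal data the disagreement is mostly t-test only (4.2%, against 1.5% Mann-Whitney only). With strong skew it is nearly all Mann-Whitney only (11.8%).

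**3. Power of the two tests on one standard.** Normal data, change SD 20:

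| | Power at 28 per arm | n per arm for 80% |
|---|---|---|
| t-test | 78.7% (exact) | 29 |
| Mann-Whitney U | about 76% (simulated) | 31 |

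Under skew Mann-Whitney U has no shortfall; with sigma 0.25 its power at 28 per arm is about 80.7%.

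**4. A linear model with arm and baseline.** The power paragraph does not say whether SD 20 belongs to the post-dose mean or to the change. Suppose it is the post-dose SD, with assumed baseline SD s of 5–20 and assumed correlation r of 0.2–0.6.

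- SD of change = √(20² + s² − 2 × r × 20 × s). At s = 20, r = 0.2: √(400 + 400 − 160) = 25.3.
- Residual SD after baseline adjustment = 20 × √(1 − r²). At r = 0.2: 19.6. At r = 0.6: 16.0.

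Exact power at 28 per arm over that grid is 80–93% for the adjusted model and 59–93% for the t-test on change. If SD 20 is instead the SD of the change, the adjusted model has 78% or more. The adjusted model gives the same treatment effect and p-value whether the outcome is the post-dose mean or the change.

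**5. Dose count.** The documents give no figures from which to size the bias, so this part rests on the order of events in step 4.

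**The case against.** **The text can be reconciled.** The Mann-Whitney sentence states an expectation about blood pressure, the general rule follows, and the end of the power paragraph applies it straight after the primary power calculation. On that reading the only gap is an unnamed normality criterion. This is the strongest defence, and part of it stands: a fixed rule would hold type I error near 5%. But the rule follows a sentence about exploring differences between groups, it overrides two unconditional assignments, and it could still send an objective about means to a test reported with medians.

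**The Mann-Whitney sentence says average BP, not systolic.** True, but averaged change from baseline is how the primary outcome is built, and no other outcome is named for it.

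**The regression as a third rival.** A reader might infer that the sponsor can pick the best of three planned results. With the regression counted as a candidate, simulated type I error reaches about 6.5–9%. The documents do not support that as the headline: the regression is given a different purpose, adjustment for confounders, and is never called primary. The figure also depends on assumed baseline SDs and correlations. What stands is that its rank should be stated.

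**The sample size.** A reader might infer that Mann-Whitney U needs 31 per arm against the planned 28. That compares an exact requirement with an approximate one. On one standard the gap is 31 against 29, and it holds only for normal data.

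**The fix goes beyond the defect.** Naming the t-test on change would also end the conflict. That is fair. The linear model is preferred because it also removes the doubt between post-dose mean and change, and protects power if baseline varies widely.

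**Conclusion.** The point holds as a conflict between stated rules, not merely as missing detail. The primary comparison has two unconditional tests, a deferred choice with no criterion, and an unranked regression.

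The effect on type I error is small, about 5.8–5.9% against 5% with normal data. The practical harm is that the plan does not say which result decides the trial. With a true 15 mmHg effect that matters in about 1 trial in 18 with normal data, and in more if the data are skewed. These figures assume 28 completers per arm and SD 20 on the change score; the skewed cases rest on shapes that the documents do not give, so the 1-in-8 figure should not be quoted without that label.

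There is no arithmetic error in the sample size. The adjustment for number of doses is a separate defect: it can bias the treatment effect, by an amount that cannot be computed from the documents. This should be fixed, and the fix is cheap.

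**What to change.** Before unblinding:

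1. Name one primary analysis: the between-arm difference in the mean of the 15, 30, 45 and 60 minute systolic readings, from a linear model with arm and baseline systolic pressure, two-sided alpha 0.05, reported in mmHg with a 95% confidence interval.
2. State which reading is the baseline. The inclusion criteria require a repeat severe reading 15 minutes later, and step 3 of Study Procedures does not say which one counts.
3. Delete the choice of test after data collection for the primary outcome.
4. Label the t-test, Mann-Whitney U and the wider regression as supportive, unable to replace the primary result.
5. Leave number of antihypertensive doses out of any model that estimates the treatment effect.

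If the sponsor prefers Mann-Whitney U as primary, restate its power at 28 per arm (about 76% with normal data and change SD 20, against 78.7% for the t-test) or revise the sample size, and say how the effect will be estimated.

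Cost: analysis wording only for the linear model. Baseline pressure is already recorded and the planned 28 per arm can stay. The sponsor gives up choosing the test after seeing the data.

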Given its potential for both significant maternal and fetal morbidity, hypertensive disorders in pregnancy comprise a substantial proportion of antepartum admissions. Management of acute severe hypertension (systolic BP≥ 160 or diastolic BP≥ 110) is important to reduce the risk of stroke, hypertensive encephalopathy, placental abruption, and heart failure or myocardial infarction⁴. In the antepartum and intrapartum period, the use of antihypertensives including labetalol, nifedipine, and hydralazine have been well-described⁴. Despite these options for blood pressure control, preeclampsia can be a progressive disorder that may not respond to the aforementioned agents.

Version 2 Protocol Number I

In preeclampsia manifested by high blood volume due to salt and water retention rather than vasoconstriction, standard antihypertensives may be less effective. Furosemide is a commonly used diuretic that can lower blood pressure by inhibiting the absorption of sodium, chloride, and water, thereby decreasing the volume of blood that the heart pumps. The onset of action of action of IV furosemide is 5 minutes, with peak effect at 30 minutes, and duration of action of 2 hours⁵.

Previous studies have demonstrated the safety and efficacy of furosemide to treat preeclampsia in the antepartum and postpartum period as well as its utility in treating heart failure in pregnant women^{6,7}. To our knowledge, no randomized studies exist that investigate the use of furosemide in treating hypertension in the antepartum period. We aim to determine the utility of the addition of furosemide to usual antihypertensives in this clinical setting.

References

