A power calculation was completed using OpenEpi, Version 3, open source calculator—SSMean. The assumption of normality and that both groups will have the same common variance was applied. We set the standard deviation value as 20mmHg in the power calculation, which is based on pilot data from our own practice as well as data found in a randomized clinical trial using furosemide versus placebo (Ascarelli et al, Ob/Gyn 2005). A 15mmHg reduction in mean systolic blood pressure in the placebo group compared with the IV furosemide group was considered to be clinically significant as this represents an attainable, yet safe reduction from severe to mild range blood pressure. Using the 2-group Student t-test of equal means, 28 patients per study arm for a total of 56 patients would be required to detect a difference of 15mmHg with 80% power and a significance level of p=0.05. Once data has been collected, we will test for normality and use the appropriate statistical tests.

To account for patients who withdraw from the study or who need to be excluded after consent, 35 per arm or 70 total patients are to be enrolled. A randomization schedule will be created using block randomization with 10 blocks of 10 participants allocating randomization numbers to drug or placebo. The numbers will be sequentially assigned to participants by the pharmacist on duty. The hospital pharmacy will maintain the master list of the randomization log with patient study identifiers.

Data monitoring

Describe data monitoring methods for studies with more than minimal risk (i.e. data monitoring committee). Explain adverse event reporting procedures.

This is a greater than minimal risk study. Adverse events will be reported to the sub-investigator and primary investigator by the nurse and/or the obstetric provider. Furthermore, the sub-investigator will be actively following study participants closely to monitor for adverse events. If found, these will be reported to the institutional review board according to their reporting polices.

3. Data storage, security, and confidentiality

Describe where data will be stored and how data will be secured during the study. Provide information on confidentiality measures (coding, storage mechanisms, etc.). Indicate who will have access to the data and how the data will be used. If subject identifiers will be released, describe to whom and for what purpose the data will be released.

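### The regression adjusts for number of antihypertensive doses, a post-randomisation variable the study drug can change, so its arm coefficient is not the total add-on effect of furosemide

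*Combined protocol and SAP*

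**What the plan says.** The primary objective (Section I.1) is the effect of adding IV furosemide to usual antihypertensives on systolic pressure, compared with adding placebo. The primary outcome (Section III.2) is the reduction in mean systolic pressure over the hour after study drug, analysed by intention to treat.

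Section III.2 also plans a multivariate regression for potential confounders. Its example covariates are maternal age, BMI, diabetes, baseline BP, and "antihypertensive chosen by the primary obstetrician, number of doses of antihypertensive, and gestational age". No counting window is given for the doses, and the coefficient is not described as a direct effect.

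Three other places fix the timing:

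- Study Procedures, step 4: when the provider orders the antihypertensive, "pharmacy notified that patient is study participant and randomizes patient by choosing from sequential opaque envelope".
- Study Procedures, step 6: "Blood pressure check every 15 minutes after administration of furosemide/placebo for four recordings", at 15, 30, 45 and 60 minutes.
- Background (Section I.2): the onset of "IV furosemide is 5 minutes, with peak effect at 30 minutes".

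Section III.1 leaves the antihypertensive to the provider and allows more than one agent. The documents contain no rule for repeat doses.

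**The concern.** In a randomised comparison, a variable that assignment can affect is not a confounder. Age, BMI, diabetes, baseline BP and gestational age are settled before the envelope is opened. The number of doses, as written, is not. If furosemide lowers pressure by the 15- or 30-minute reading, fewer furosemide patients may need another dose. Comparing patients with equal dose counts then removes part of what furosemide did. It also compares unlike patients: someone on placebo who needed only one dose is likely to be a good responder to the first antihypertensive.

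Patients remain in their randomised arms, but the arm coefficient answers a different question from the stated objective. A real benefit could be reported next to a clearly smaller figure labelled as adjusted for confounders, and readers could take the gap as evidence of chance imbalance between arms. The protocol does not rank the regression against the t-test and the Mann-Whitney test, so nothing tells the reader which figure to trust.

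**Working it through.** **1. The plan's own figure.** Inputs from Section III.2: "We set the standard deviation value as 20mmHg in the power calculation"; "28 patients per study arm for a total of 56 patients would be required to detect a difference of 15mmHg with 80% power"; two-sided 0.05.

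n per arm = 2(1.960 + 0.842)² × 20² / 15² = 2 × 7.85 × 400 / 225 = 27.9, so 28 per arm and 56 in total. Power at 28 is 80.1% by the normal approximation. With 80% retention, 56 / 0.80 = 70. The figure reproduces. No covariate enters it, so the concern does not touch it.

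**2. Why the two coefficients differ.** For least squares with baseline in both models, an exact identity holds:

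arm effect without doses = arm effect with doses + γ × δ

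Here γ is the dose-count coefficient and δ is the arm difference in dose count at equal baseline. The two agree only if γ or δ is zero.

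An illustration with assumed inputs: baseline mean 170, direct effect 15 mmHg, between-patient response SD 17, and a repeat dose given with probability 0.9 when a reading reaches a simulated trigger. The outcome is the reduction in pressure.

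- Repeat doses have no effect, trigger 150: mean doses 2.12 on furosemide and 2.87 on placebo, δ = −0.75, γ = −11.5, γδ = 8.6. Adjusted 6.4 + 8.6 = total 15.0.
- Each repeat dose lowers pressure by 10 mmHg, trigger 160: mean doses 1.45 and 2.03, δ = −0.58, γ = −10.9, γδ = 6.3. Adjusted 5.8 + 6.3 = total 12.2 after rounding.

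In the first case repeat doses do nothing, yet each extra dose goes with an 11.5 mmHg smaller reduction. The count is marking poor responders. The adjusted figure (6.4) is therefore not the direct effect (15) either.

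**3. Size at the protocol's design figures.** The models were 1-hour mean SBP on arm and baseline, with and without dose count, in 48 scenarios of 300,000 patients.

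From the protocol: total effect 15 mmHg and SD 20 mmHg, the SD being read here as the placebo SD of change.

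Assumed:
- baseline normal (mean 160, SD 12) truncated at 160;
- first dose lowers SBP by 10, 15 or 20 mmHg;
- first dose and furosemide at half effect at 15 minutes and full effect from 30;
- reading-to-reading SD 8;
- repeat-dose effect 0, 4, 8 or 12 mmHg;
- between-patient SD (19.6–25.4) and direct effect (17.1–20.9) tuned to hit the two design figures.

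| Share of readings ≥160 (at 15, 30 or 45 min) followed by a repeat dose | Without dose count (mmHg) | With dose count (mmHg) | Reduction |
|---|---|---|---|
| 25% | 15.0 | 12.3–13.0 | 14–18% |
| 50% | 15.0 | 9.8–10.7 | 28–35% |
| 75% | 15.0 | 7.4–8.9 | 41–51% |
| 100% | 15.0 | 5.1–7.6 | 50–66% |

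Percentages are taken against each scenario's own simulated total, so they can differ by about a point from the rounded mmHg figures.

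**4. No furosemide effect.** With the direct effect set to zero, the adjusted estimate stays within 0.1 mmHg of zero, because δ is then zero.

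**5. Direction.** With between-patient SD of only 0–5 mmHg (SD of change about 4–6), the adjusted estimate ranged from 33% smaller to 17% larger than the total effect.

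A pure mediator, sharing no cause with pressure, always pushes upward. Take a direct effect of 15, 5 mmHg per dose and three chances of a repeat dose, each with probability 0.5 on placebo. With probability 0.3 on furosemide the total is 15 − 5 × 3 × 0.2 = 12.0; with 0.2 it is 15 − 5 × 3 × 0.3 = 10.5. The adjusted estimate is about 15 in both.

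**The case against.** The strongest objection is that repeat dosing within the hour is inferred. The documents give no trigger, frequency or counting window, and nothing in the eligibility criteria excludes earlier antihypertensive doses, so the count might have been meant to cover doses before randomisation. If so, the concern falls. But the text does not say so. Study drug is given alongside the antihypertensive ordered at randomisation, so a count that varies between patients most naturally reflects later doses.

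Several lesser points stand as limits:

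- The protocol does not say what its 20 mmHg is the SD of. Assigning most of it to stable differences between patients increases the attenuation. At between-patient SD 10 and 25% redosing the shift is 4–12%, not 14–18%.
- At 25% redosing the shift of 2.0–2.7 mmHg is about half the standard error of the planned comparison, 20 × √(2/28) = 5.3 mmHg. The 100% row is an extreme.
- An overstated effect is possible, as step 5 of the working shows.
- The covariate list is introduced as examples, so dose count could be dropped without departing from the plan. As written, it is named.

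One might also argue that adjusting isolates furosemide's own effect. It does not: dose count and outcome share a cause in patient responsiveness, and ordinary regression does not remove that.

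**Conclusion.** The concern holds: the covariate is wrong as written. Dose count, with no window, is settled at least partly after randomisation and can depend on pressure the study drug has changed, so adjusting for it does not give the total add-on effect named in the objective. This structural conclusion rests on the protocol's own timing and on some repeat doses falling within the outcome hour.

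The size depends on assumptions the documents do not supply. At the protocol's SD, if furosemide works, the likely result is an understated benefit, by roughly one-seventh to two-thirds depending on how often high readings lead to another dose. If patients vary much less than the SD implies, the estimate can move either way. There is no sign of a false positive when furosemide has no effect. The unadjusted tests and sample size are sound on this point, so it should be fixed but does not threaten the main comparison.

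**What to change.** Before unblinding, replace the covariate sentence in Section III.2 with: *Multivariate regression will adjust only for variables fixed before the randomisation envelope is opened: maternal age, BMI, diabetes, baseline BP, gestational age, and the first antihypertensive ordered.* Where several agents are ordered together at that moment, the covariate can be defined as that set.

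Delete the number of antihypertensive doses from the list, and describe the dose count in the hour after study drug by arm as a post-randomisation result. If the investigators meant only doses given before the envelope is opened, a count defined that way could stay, provided the text says so.

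The cost is one sentence of analysis wording. It needs no new data and leaves the 28 per arm, the 70 enrolled, the unadjusted tests and clinical management unchanged.

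### The 80% power at 28 per arm is a normal-approximation figure labelled as a t-test; the t-test gives 78.7%, and the Mann-Whitney test also named for the comparison is not powered

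*Combined protocol and SAP*

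**What the plan says.** All the relevant text is in the combined protocol and SAP, mostly in Section III.2 (Data analysis).

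- **Primary outcome and first test.** The outcome is the reduction in mean systolic BP over the hour after dosing, from averaged 15-minute readings. The plan says "Intention-to-treat analysis will be performed" and "This study will use a two-sided t-test with the null hypothesis set at the standard significance level".
- **Second test.** The next paragraph says "Change in average BP from baseline will be tested comparing the group receiving furosemide and the group receiving placebo using Mann-Whitney U", with the reason "as BP usually presents as a non-parametric continuous variable". Section I.1 (Purpose) words the primary objective as a reduction in mean systolic BP from baseline, so this is essentially the primary comparison again.
- **Power.** The calculation uses SD 20 mmHg and a 15 mmHg difference. It states that "The assumption of normality and that both groups will have the same common variance was applied" and, by the two-group Student t-test, that "28 patients per study arm for a total of 56 patients would be required", with "80% power and a significance level of p=0.05".
- **Choice of test.** The power paragraph closes by saying that normality will be tested once data are in and the test chosen accordingly.
- **Numbers.** Enrolment is 35 per arm (70 in total), to allow for withdrawals and for exclusions after consent. Section II.1 expects about 80% retention, that is, 56 completers.

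**The concern.** A stated power belongs to a particular test, applied to a particular number of patients, under stated assumptions. Here the label and the calculation differ: the figure is attributed to a t-test but comes from a formula that treats the SD as known. The plan also leaves three routes open for one comparison (t-test, Mann-Whitney, or whichever a normality check selects) and gives power for only one of them. The sizing assumes normal data, while Mann-Whitney is justified by expecting data that are not normal.

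If the result is not significant, readers will be told that the trial had 80% power for 15 mmHg. On the plan's own inputs, neither named test reaches that at 28 per arm. The more important matter is that the test behind the primary p-value is not fixed before the data are seen, so the power that goes with it cannot be stated either.

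**Working it through.** **Inputs (Section III.2).** Difference 15 mmHg; SD 20 mmHg; standardised difference 15/20 = 0.75; two-sided alpha 0.05; target power 80%; 1:1 allocation; normal data with equal variances.

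**1. The plan's own figure.** The normal-approximation formula is

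n per arm = 2 × (z₀.₉₇₅ + z₀.₈₀)² × (SD/difference)² = 2 × (1.960 + 0.842)² × (20/15)² = 2 × 7.851 × 1.778 = 27.9, rounded up to 28.

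Power at 28 by the same approximation: 0.75 × √(28/2) = 2.806, and Φ(2.806 − 1.960) = Φ(0.846) = 80.1%. The stated number therefore reproduces by this formula.

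**2. The test the plan cites.** For the Student t-test, the noncentral t distribution has 2n − 2 degrees of freedom and noncentrality 0.75 × √(n/2).

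| Per arm | t-test power |
|---|---|
| 28 | 78.7% |
| 29 | 80.1% |
| 35 | 87.1% |

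The shortfall against the approximation at 28 per arm is 80.1 − 78.7 = 1.4 points.

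**3. Mann-Whitney under the plan's assumptions.** These figures come from simulating normal data with a shift of 0.75 SD, 100,000 trials per row.

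| Per arm | No continuity correction | With continuity correction |
|---|---|---|
| 28 | 76.6% | 76.1% |
| 30 | 79.4% | 79.0% |
| 31 | 80.7% | 80.2% |
| 35 | 85.3% | 85.3% |

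As a cross-check, the asymptotic relative efficiency of 3/π makes 28 per arm worth 28 × 0.955 = 26.7 per arm to a t-test, which gives 76.8%. So about 31 per arm are needed for 80%. Moving from the t-test to Mann-Whitney costs 78.7 − 76.6 = 2.1 to 78.7 − 76.1 = 2.6 points. The rest of the gap from 80.1% is the 1.4 points in step 2.

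**4. Mann-Whitney on non-normal data.** The documents give no shape, so the shapes below are assumptions. SD, shift and 28 per arm are unchanged.

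| Shape | Mann-Whitney power |
|---|---|
| Uniform | 72–73% |
| Logistic | 81% |
| Gamma, shape 4 | 83% |
| t, 5 df | 85–86% |
| Laplace | 88% |
| Lognormal, sigma 0.5 | 90–91% |

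**5. Choosing the test after a normality check.** The plan does not name the check. Taking Shapiro-Wilk on residuals as an assumption, with 28 per arm and 10,000 trials per shape, about 95% of normal data sets go to the t-test and power is about 79%. For other shapes the rule gives about 74% (uniform), 83–84% (gamma), 84% (t, 5 df) and 90–91% (lognormal).

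**6. Number analysed.** 70 × 0.80 = 56, or 28 per arm, is the completer count. The 35-per-arm figures in steps 2 and 3 apply only if all 70 are randomised and have outcome data.

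**The case against.** The plan claims 80% only for the t-test, and the number reproduces to within 1.4 points. A reader might infer that the protocol promises 80% for Mann-Whitney and misses it, or that the trial's power is really 76%. The documents support neither. The power paragraph ties its figure to the t-test and to normal data. Mann-Whitney is chosen because normality is doubted, so the 76% combines a test and a distribution that the plan keeps apart. For most of the non-normal shapes tried, Mann-Whitney exceeds 80%. If the normality check decides, normal data go almost always to the t-test and power returns to about 79%. All of this stands, and it is why the 76% must carry its condition.

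A second objection is that intention-to-treat on 35 per arm gives 85–87%, so 80% is conservative. That holds only as an upper bound. The plan expects withdrawals and exclusions after consent. Randomisation comes after consent, so some of the 70 may never be randomised. Section III.5 (Transition from research participation) stops data collection on those who terminate.

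What the objections do not remove is that the t-test label is slightly wrong, that Mann-Whitney is named for change from baseline without any condition, and that no single primary test is fixed.

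**Conclusion.** The point holds in a limited form. At 28 per arm, with a 15 mmHg difference, SD 20, two-sided 0.05 and normal data, power is 78.7% for the t-test and about 76% for Mann-Whitney. The shortfall against 80% is 1 to 4 points, or 1 to 3 more analysed patients per arm. Off normality, Mann-Whitney power at 28 per arm ran from 72% to 91% over the assumed shapes, so no single figure can be given for the situation in which the plan expects to use that test.

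A reader might go on to conclude that the trial is underpowered or should enrol more. The documents do not support that: the gap is small, and enrolment of 70 leaves room above 56. The substantive defect is that two tests and a data-driven choice serve one comparison while power is stated for only one of them.

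**What to change.** Make these changes in Section III.2, without increasing enrolment:

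1. Name one primary test for the between-group comparison of systolic BP change from baseline, and drop the choice by normality check for that outcome. The other test can be kept as a labelled sensitivity analysis.
2. Restate power for the named test at 28 analysed per arm: about 79% for the t-test, or about 76% for Mann-Whitney if the data are normal. If Mann-Whitney is chosen, add that its power under non-normality depends on a shape not yet specified.
3. State that if all 35 per arm are randomised and have outcome data under intention-to-treat, power is at most about 87% (t-test) or 85% (Mann-Whitney, normal data).

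The cost is a few sentences and a slightly less favourable stated power for 56 patients.
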